8.1.3. Analyses of Continuous Efficacy Data

Continuous data (ie, change from baseline) will be summarized.

Repeated measures data for continuous endpoints will be analyzed as change from baseline with a mixed model for repeated measures (MMRM) that includes fixed effects of treatment group, visit, treatment-group by visit interaction, baseline value, and baseline-value by visit interaction, without imputation for missing values. A common unstructured variance-covariance matrix will be used, provided the model converges, otherwise an alternative covariance structure, eg, heterogeneous compound symmetry (CSH), will be attempted. The Kenward-Roger degrees of freedom approximation will be used. Least squares means [LSM] of the treatments, LSM of the treatment difference, 2-sided p-value and 95% CI at each time point will be generated using this MMRM. If the Baseline is missing or if there are no post-baseline measurements, the subject will be excluded from this analysis.

8.1.4. Analyses of Binary Efficacy Data

Binary data will be summarized and compared between two treatment groups using the normal approximation of binomial proportions and 95% CI of treatment difference will be constructed. The normal-approximation to the test statistic for the difference in binomial random variables is calculated as:

$$Z_i = \frac{\hat{p}_i - \hat{p}_c}{\sqrt{\frac{\hat{p}_i(1-\hat{p}_i)}{n_i} + \frac{\hat{p}_c(1-\hat{p}_c)}{n_c}}}$$

where \hat{p} refers to the relative frequency, n to sample size, the subscripts i and c refer to two treatment group.

Two-sided 95% CIs are formed by:

$$(\hat{p}_i - \hat{p}_c) \pm 1.96 \sqrt{\frac{\hat{p}_i(1-\hat{p}_i)}{n_i} + \frac{\hat{p}_c(1-\hat{p}_c)}{n_c}}$$

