6.3. Visit 1, Baseline Visit (Day 1)

Subjects are required to fast for at least 6 hours prior to the visit. Subjects who have met all the inclusion criteria and have no exclusion criteria present may participate in the study.

Procedures that will be performed prior to the first dose of study drug include:

- Physical assessment including assessment of new physical findings, weight and vital signs.
- Review of inclusion/exclusion criteria.
- Fasting laboratory testing including blood chemistry, hematology, CRP, lipid profile.
- Pregnancy testing must be completed for all women of child-bearing potential: all subjects must test negative; confirmation and documentation of the use of a highly effective method of contraception by sexually active subjects of child-bearing potential must be done (for Canada, please refer to [Appendix 6](#) for specific contraception requirements).

- Banked biospecimen sample.
- 28 tender /painful and swollen joint counts.
- Completion of the following assessments:
 - Patient assessment of arthritis pain.
 - Patient global assessment of arthritis.
 - Physician global assessment of arthritis.
 - HAQ-DI.
 - SF-36 (Version 2, Acute).
 - EuroQol EQ-5D.
 - Work Productivity and Activity Impairment (WPAI) Questionnaire.
- Safety Assessment and AE Reporting.
- Concomitant Medication Review.
- Confirm that all screening procedures have been completed and the subject is eligible for randomization.
- Randomize and dispense study medication as identified by the randomization/drug dispensing system.
- Schedule the subject to return for Visit 2 (Month 2).

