6.4. Covariates

The following demographic variables will be included as covariates in the multivariate Cox proportional hazard model:

Geographic regions:

4 levels: USA/Canada, Europe, Latin America, and rest of world.

Age:

In years (to the nearest year) at entry to the study (categorized as 50 to <65, 65 to <75, ≥ 75).

Smoking:

Current or ex-smoker, lifetime nonsmoker.

Gender:

Male and Female.

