8.2.3. Analyses of Efficacy Endpoints

All efficacy analyses will be based on the Full Analysis Set.

Descriptive statistics of efficacy endpoints for all subjects in the study will be provided from baseline to the declared end of the study. Differences between each tofacitinib regimen (5 mg BID, 10 mg BID, or combined) and the TNFi regimen as well as between tofacitinib regimens will be estimated. The difference estimates will be derived based on the following models:

- Analysis of continuous data, ie, change from baseline in DAS28-4(CRP), SDAI, CDAI, HAQ-DI will be analyzed using 95% CI of treatment difference based on MMRM analysis. (See discussions in [Section 8.1.3](#)).
- Dichotomized data will be summarized and compared between treatment groups using the normal approximation of binomial proportions and 95% CI of treatment difference (see discussions in [Section 8.1.4](#)). This approach will be used for the following efficacy variables:
 - Rate of remission: ACR-EULAR Boolean remission, SDAI ≤ 3.3 , CDAI ≤ 2.8 .
 - Rate of low disease activity (LDA): SDAI ≤ 11 , CDAI ≤ 10 , DAS28-4 (CRP) ≤ 3.2 .
 - ACR20, ACR50, and ACR70 response rate.

For efficacy analyses, the treatment groups will be tofacitinib 5 mg BID, tofacitinib 10 mg BID, and TNFi regimen.

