Appendix 1.4. Further Definition of Endpoints

Indicator	Definition/Calculation
DAS28-4 (CRP)	$DAS28-4(CRP) = 0.56 * \sqrt{TJC28} + 0.28 * \sqrt{SJC28} + 0.36 * \ln(CRP+1) + 0.014 * PtGA + 0.96$
Simplified Disease Activity Index (SDAI)	$(TJC28) + (SJC28) + PhyGA/10 + PtGA/10 + CRP/10$
Clinical Disease Activity Index (CDAI)	$(TJC28) + (SJC28) + PhyGA/10 + PtGA/10$
American College of Rheumatology (ACR) Response Rates	The ACR’s definition for calculating a 20% improvement in RA (ACR20) is as follows: a 20% improvement in tender and swollen joint counts and 20% improvement in 3 of the 5 remaining ACR-core set measures: patient and physician global assessments, pain, disability, and an acute-phase reactant (eg, CRP). Similarly, ACR50, 70 and 90 are calculated with the respective percent improvements.
ACR/EULAR Boolean-based definition of remission	subject must satisfy all of the following: $TJC28 \leq 1, SJC28 \leq 1, CRP \leq 10, PtGA \leq 10$

where TJC28 is number of painful joints out of 28 joints; SJC28 is number of swollen joints out of 28 joints; PtGA is the patient’s global assessment of disease activity on a 100 mm VAS; PhyGA is the physician’s global assessment of disease activity on a 100 mm VAS; CRP = C-reactive protein in mg/L; ln is the natural logarithm; sqrt is square root

Patient’s Global Assessment of Health: Subjects will answer the following question, “Considering all the ways your arthritis affects you, how are you feeling today?” The subject’s response will be recorded using a 100 mm visual analog scale (VAS).

Physician’s Global Assessment of Health: The investigator will assess how the subject’s overall arthritis appears at the time of the visit. This is an evaluation based on the subject’s disease signs, functional capacity and physical examination, and should be independent of the Patient’s Global Assessment of Arthritis. The investigator’s response will be recorded using a 100 mm visual analog scale (VAS).

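### Five remission and low-disease-activity endpoints are compared without baseline adjustment although the same indices are baseline-adjusted as continuous outcomes; the analysis is valid but slightly less precise than it need be

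*SAP*

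**What the plan says.** For binary efficacy data, SAP 8.1.4 gives an unadjusted difference in proportions with an unpooled normal-approximation 95% interval: "Binary data will be summarized and compared between two treatment groups using the normal approximation of binomial proportions". SAP 8.2.3 applies that method to all nine dichotomized endpoints (three remission, three low disease activity, and ACR20/50/70): "Dichotomized data will be summarized and compared between treatment groups using the normal approximation of binomial proportions and 95% CI of treatment difference". It names no covariate, stratification factor or adjusted sensitivity analysis.

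For change in DAS28-4(CRP), SDAI, CDAI and HAQ-DI, SAP 8.1.3 specifies a repeated-measures model that "includes fixed effects of treatment group, visit, treatment-group by visit interaction, baseline value, and baseline-value by visit interaction".

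SAP 6.4 lists region, age, smoking and gender, but for the safety model only: "The following demographic variables will be included as covariates in the multivariate Cox proportional hazard model". Protocol 9.3 says that differences between regimens will be estimated and leaves the details to the SAP.

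Protocol 6.3 has the index components recorded before the first dose: "28 tender /painful and swollen joint counts", the patient and physician global assessments, and CRP. SAP 7.2 allows for a missing baseline by counting the subject as a non-responder.

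**The concern.** Five binary endpoints are cut-points of indices that the plan also analyzes as continuous outcomes: SDAI at 3.3 and 11, CDAI at 2.8 and 10, DAS28-4(CRP) at 3.2. The continuous analysis removes the part of the outcome that baseline disease activity predicts. The threshold analysis leaves it in the error, and the documents give no reason for the difference.

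Two modest things are at stake. The intervals for these five endpoints, at every visit, are wider than the data already collected would allow. And a chance imbalance in baseline activity moves the threshold result but is largely removed from the continuous result for the same index.

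**Working it through.** **1. The plan's own figures.** The only sizing in the documents is for the co-primary safety endpoints (Protocol 9.1). With D = (z₀.₉₇₅ + z_power)² / [a(1−a)(ln margin)²], where a is the allocation fraction:

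- Margin 1.8, a = 2/3: 137 events at 90% power (plan 138) and 103 at 80% (plan 103).
- Margin 2.0, a = 1/2: 88 at 90% (plan 87) and 66 at 80% (plan 65).

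These agree to within one event. No size or power is stated for efficacy, so nothing below depends on them.

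**2. Inputs for the efficacy check.** From the documents: n = 1300 per arm and the SAP 8.1.4 interval. Assumed, because the documents give neither: a common response rate p of 10%, 30% or 50%, and a latent-normal correlation ρ of 0.2 to 0.5 between baseline and the visit value.

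**3. Formulas.**

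- Planned half-width: 1.96·√(2p(1−p)/1300). At p = 0.30 this is 1.96·√(0.42/1300) = 0.0352.
- Share of response variance explained by baseline: R² = [ρ·φ(z_p)]² / [p(1−p)], with φ the normal density at the p-quantile. At p = 0.30 and ρ = 0.3: (0.3 × 0.3477)² / 0.21 = 0.0518.
- Adjusted half-width: planned × √(1−R²). Effective n per arm: 1300/(1−R²).

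| p | Planned half-width (points) | ρ | R² | Adjusted half-width (points) | Narrower by | Effective n per arm |
|---|---|---|---|---|---|---|
| 10% | 2.31 | 0.2 | 0.0137 | 2.29 | 0.7% | 1318 |
| 10% | 2.31 | 0.3 | 0.0308 | 2.27 | 1.6% | 1341 |
| 10% | 2.31 | 0.5 | 0.0856 | 2.21 | 4.4% | 1421 |
| 30% | 3.52 | 0.2 | 0.0230 | 3.48 | 1.2% | 1330 |
| 30% | 3.52 | 0.3 | 0.0518 | 3.43 | 2.6% | 1371 |
| 30% | 3.52 | 0.5 | 0.1439 | 3.26 | 7.5% | 1518 |
| 50% | 3.84 | 0.2 | 0.0255 | 3.79 | 1.3% | 1333 |
| 50% | 3.84 | 0.3 | 0.0573 | 3.73 | 2.9% | 1379 |
| 50% | 3.84 | 0.5 | 0.1592 | 3.52 | 8.3% | 1546 |

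The percentage narrowing depends on R² and not on n.

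**4. Simulation check.** Standardized logistic regression on treatment and baseline was compared with the raw difference: 1300 per arm, a latent treatment shift of 0.1, 1500 replicates per case. The variance ratio, adjusted over raw, at p = 10%, 30% and 50% was:

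- ρ = 0.3: 0.954, 0.940, 0.933.
- ρ = 0.5: 0.890, 0.835, 0.848.

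These are close to 1−R² from the table (0.969, 0.948, 0.943 and 0.914, 0.856, 0.841). The mean estimates agreed to within 0.0004 in every case (for example 0.0350 raw and 0.0351 adjusted), so both methods estimate the same quantity.

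**5. Chance imbalance.** The standardized baseline difference between two arms has a 95% limit of 1.96·√(2/1300) = 0.077 SD. At p = 30% that moves the raw difference by about ρ × 0.3477 × 0.077, which is 0.5 points at ρ = 0.2 and 1.3 points at ρ = 0.5. The planned half-width is 3.5 points.

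**6. Which endpoints gain.** In an illustrative model (assumed: log-normal CDAI, medians 35 at baseline and 11 at the visit, log-SDs 0.35 and 0.8, ρ 0.2 to 0.5), log baseline explains 2.5% to 15.8% of the variance of CDAI ≤10 and 0.8% to 5.0% of CDAI ≤2.8. For a 50% or 70% improvement in the index, used as a stand-in for ACR response, it explains only 0.3% to 3.5%.

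**The case against.** The strongest reply is that nothing here is an error. In a randomized comparison the raw risk difference is unbiased with a valid interval, efficacy is secondary (SAP 6.1), and the decision rules in SAP 4.2 concern safety alone. All of that stands, and it limits the point to precision.

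The gain also rests on assumed correlations. Entry requires at least 6 tender and 6 swollen joints (Protocol 4.1), which restricts the baseline range and may put the true correlation at the low end. That stands too.

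Nor would adjustment make the two analyses of one index agree. They also differ through thresholding and through missing data: component-wise carry-forward for binary endpoints, no imputation in the repeated-measures model (SAP 7.2). Adjustment removes one source of disagreement only.

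A reader might infer three stronger things that the documents do not support:

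- **That all nine binary endpoints share the inconsistency.** ACR20/50/70 and Boolean remission have no continuous version in the plan, and ACR response already contains the subject's own baseline, being defined through "a 20% improvement in tender and swollen joint counts" and similar relative changes.
- **That the data safety monitoring board's view of the 10 mg BID arm was affected.** Its recommendation had reached investigators by 19 February 2019 (Protocol 1.2), and SAP section 3 leaves monitoring analyses to the committee's charter. SAP 8.1.4 governs the final analysis.
- **That region must be added because it determines the TNFi.** Region is a covariate of the safety model only, and the repeated-measures model omits it. Adding it to the binary model alone would create a new mismatch.

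**Conclusion.** The point holds as a small precision improvement for five secondary endpoints. Within the assumed ranges (latent correlation 0.2 to 0.5, response rate 10% to 50%), intervals would be about 1% to 8% narrower, equivalent to 18 to 246 additional subjects per arm. At a correlation of 0.3 the figure is 1.6% to 2.9%. In absolute terms the half-width falls by between 0.02 points (2.31 to 2.29) and 0.32 points (3.84 to 3.52).

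It would be wrong to read this as bias, a faulty interval or an inflated error rate: the planned estimator is sound. No primary safety conclusion changes. The case for acting is that the gain needs no new data and leaves the estimated quantity unchanged.

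**What to change.** In SAP 8.1.4 and 8.2.3, before database release, specify the following for the SDAI, CDAI and DAS28-4(CRP) threshold endpoints:

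- Estimate the marginal risk difference at each visit by standardization (g-computation) from a logistic model with treatment and the baseline value of the index, with a delta-method or bootstrap 95% interval. State how the combined-tofacitinib contrast is formed.
- Keep subjects with a missing baseline in the analysis as non-responders, as SAP 7.2 already requires, and fill their baseline covariate with the mean pooled across arms. The population and estimand then do not change. A missing-baseline indicator is less convenient: these subjects are all non-responders by rule, so the indicator would predict the outcome perfectly.
- Keep the raw proportions by arm as descriptive output.

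Adjustment for region is optional; if it is wanted, add it to the repeated-measures model as well. Extension to ACR20/50/70 and Boolean remission is also optional, with little gain expected for ACR. Boolean remission has no single baseline index, so its baseline components would have to be named.

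The cost is a paragraph of SAP text, including the missing-baseline rule, and standard programming. No new data, visits or subjects are needed.

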8.2. Statistical Analyses

As of 19 February 2019, the tofacitinib 10 mg BID treatment arm reduced dosing to tofacitinib 5 mg BID; all analyses identified for the tofacitinib 10 mg BID treatment arm will be conducted as stated even though subjects in that treatment arm reduced their prescribed dose. Specifically, all references to the Tofacitinib 10 mg BID arm will include subjects randomized to tofacitinib 10 mg BID and discontinued study drug prior to Amendment 8 and those subjects who were randomized to tofacitinib 10 mg BID and had their dose of tofacitinib reduced to 5 mg BID with Protocol Amendment 8.

8.2.1. Primary Analysis

Safety endpoint analyses will be carried out using the data collected on the Safety Analysis Set.

Two methods in defining time to an event will be used for the co-primary time-to-event safety endpoints: 60-Day On-Treatment Time and Total Time (see [Section 7.1.1](#) for definitions). The 60-Day On-Treatment Time definition will be used for primary MACE analysis. The Total Time definition will be used for primary malignancies (excluding NMSC).

This primary objective will be addressed via the analysis of the times to these events by proportional hazard (Cox) models via univariate model analysis. See details in [Section 8.1.1](#).

In the time-to-event analyses using a Cox model, the treatment groups will be tofacitinib 5 mg BID, tofacitinib 10 mg BID, and TNFi regimen (adalimumab 40 mg QOW SC and etanercept 50 mg QW SC combined).

Ninety-five percent CIs for the hazard ratios for the combined tofacitinib regimens compared to the TNFi regimen as well as for the 3 pair-wise treatment comparisons, tofacitinib 10 mg BID vs. tofacitinib 5 mg BID, tofacitinib 5 mg BID vs. TNFi, tofacitinib 10 mg BID vs. TNFi, will be presented. For this analysis, only treatment group will be used as an independent variable in the model. For the Total Time analyses changes from original randomized treatment will be ignored. For the 60-Day On-Treatment Time analyses, rules for censoring times to event due to switching from randomized treatment to standard of care are given in [Section 7](#).

Further, multivariate analysis and analysis by TNFi subset strata (ie, the sites/regions where either adalimumab or etanercept was used, in other words, USA/Puerto Rico/Canada as one stratum, the rest as the other stratum) will be conducted to assure consistency of results. No additional analyses comparing adalimumab vs. etanercept will be conducted for the purpose of reporting the primary endpoints of the study; when reporting the primary endpoint analyses, any difference in hazard ratio between the two TNFi controls will be attributed to geographic difference.

These analyses will be used to check the robustness and to assure consistency of the results for primary safety endpoints:

- Models containing independent variable of treatment group adjusted with geographic region, age group, gender, and smoking status (see covariates in [Section 6.4](#)) will be fitted using Safety Analysis Set.
- *An analysis by TNFi subset strata (ie, the sites/regions where either adalimumab or etanercept was used)* will be performed using Safety Analysis Set.
- The same analyses conducted based on Safety Analysis Set will be conducted using Per Protocol Analysis Set.

Unadjusted, or “crude” incidence rates by Total Time, 60-Day On-Treatment Time and 28-Day On-Treatment Time analysis will be calculated as well.

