This Post-Authorization Safety Study (PASS) was developed in response to the requirements of the US Food and Drug Administration to further define the safety profile of tofacitinib 5 mg BID and 10 mg BID, especially with respect to major adverse cardiovascular events (MACE) and malignancies, and to provide comparative safety analyses to a TNF inhibitor in an open-label manner.

The subcutaneously self-administered TNFi's, adalimumab and etanercept, will be included in this study. Subjects randomized to receive TNFi in the United States (US), Puerto Rico and Canada will receive adalimumab; in all other countries, subjects randomized to receive TNFi will receive etanercept.

Based on the totality of the non-clinical and clinical data generated thus far, identified risks associated with tofacitinib include infection, lipid elevations, anemia, neutropenia and malignancies. The identified risks for the completed studies with tofacitinib in RA are presented in the XELJANZ™ (tofacitinib citrate) Investigator Brochure.

New safety information about tofacitinib was provided to Study A3921133 investigators on 19 February 2019. That information stated that Pfizer received communication from the Tofacitinib Rheumatology Data Safety Monitoring Board (DSMB) stating that on the basis of the data reviewed thus far in Study A3921133, there is a statistically and clinically important difference in the occurrence of pulmonary embolism within the tofacitinib 10 mg BID treatment arm compared to the TNFi control arm, and the overall incidence per person year in the tofacitinib 10 mg BID arm is substantially higher than the TNFi control arm and substantially higher than observed in other studies across the tofacitinib program. Additionally, the DSMB noted an increase in all-cause mortality in the 10 mg BID arm compared to the tofacitinib 5 mg BID and TNFi treatment arms.

Based on the totality of evidence including a review of selected efficacy parameters and a finding of only minor increments in efficacy with tofacitinib 10 mg BID beyond the efficacy seen in the 5 mg BID group, the DSMB further stated that continued treatment with tofacitinib 10 mg BID in Study A3921133 entails a risk that is not sufficiently balanced.

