3. STUDY DESIGN

This is a Phase 3b/4 randomized, parallel arm, open-label safety endpoint study. All subjects will be randomized in a 1:1:1 ratio to one of the three treatment arms with approximately 1300 subjects in each treatment arm:

1. Tofacitinib 5 mg BID (oral).
2. Tofacitinib 10 mg BID (oral).*
3. TNFi: In the US, Puerto Rico and Canada, subjects randomized to TNFi will receive adalimumab 40 mg every other week (QOW) by subcutaneous injection (SC); in all other countries, subjects randomized to TNFi will receive etanercept 50 mg once weekly by SC injection.

* In response to new safety information about tofacitinib that was provided to Study A3921133 investigators on 19 February 2019, investigators were notified to verbally inform subjects randomized to tofacitinib 10 mg BID to reduce the dose of tofacitinib to 5 mg BID within 7 calendar days of this notification, secure their verbal agreement to continue in the study, and if they agreed, reduce their dose of tofacitinib to 5 mg BID for the remainder of the study. Tofacitinib is supplied as 5 mg tablets, which allowed subjects to decrease from their previous dose of 2 tablets twice daily to 1 tablet twice daily.

During the study, subjects may require alternate therapies in addition to, or instead of, their randomized drug assignment. All subjects, regardless of their treatment regimen will participate in the study until study completion. (See [Sections 5.6.1](#) and [6.5](#)).

[figure not shown]
Study completion will be declared when all 3 of the following conditions are met:

1. At least 1500 subjects have been followed for at least 3 years.
2. The targeted number of MACE are observed (See [Section 9.2.1](#)).
3. The targeted number of malignancies excluding non-melanoma skin cancers are observed (See [Section 9.2.1](#)).

It is expected that approximately 4000 subjects will participate in the study and the expected duration of the study is approximately 5 years following randomization of the first subject. The exact number of subjects and duration of the study will be determined by the pre-specified rules outlined in the charter of the blinded Steering Committee. (See [Section 9.6](#))

The study design schematic for the study is represented in [Figure 1](#).

Figure 1. Study Design (Minimum 1300 Per Arm, Total N=4000)

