4.2. Statistical Decision Rules

The hazard ratios relative to the TNFi control regimen for the tofacitinib regimens will be estimated together with 95% two-sided confidence intervals (CI). Non-inferiority of tofacitinib regimens to TNFi control regimen will be concluded if the upper confidence limits for both malignancy (Total Time Analysis) and MACE (60-Day On-Treatment Time Analysis), are less than 1.8.

Additionally, hazard ratios of tofacitinib 10 mg BID vs. tofacitinib 5 mg BID along with 95% two-sided CIs will be estimated. Non-inferiority of tofacitinib 10 mg BID to tofacitinib 5 mg BID will be concluded if the upper confidence limits for both malignancy (Total Time Analysis) and MACE (60-Day On-Treatment Time Analysis) are less than 2.0.

Adjustments for multiplicity will not be applied.

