For the **60-Day On-Treatment Time Analyses** of time-to-event, in addition to the foregoing, when a subject changes from the randomized study treatment to standard of care, the subject’s time to event will be considered censored (censoring time = last dose day of randomized study regimen + the attribution window, or the study day of last on-study contact, whichever is earlier). It will be used for the primary safety endpoint MACE but excluding malignancy (excluding Non-melanoma Skin Cancer (NMSC)), and the attribution window will be 60 days. In other words, the censoring time will be the earliest of study day of last on-study contact, study day of death, and last dose day of randomized study regimen plus 60 days.

For the **Total Time Analyses** of time-to-event, the censoring time will follow the four foregoing listed cases, ie, the censoring time will not change when a subject changes from the randomized study treatment to standard of care. In other words, the censoring time will be the earlier of study day of last on-study contact and study day of death.

For the **28-Day On-Treatment Time Analyses** of time-to-event, in addition to the foregoing, when a subject changes from the randomized study treatment to standard of care, the subject's time to event will be considered censored (censoring time = last dose day of randomized study regimen + the attribution window, or the study day of last on-study contact, whichever is earlier). It will be used for all the secondary safety endpoints, and the attribution window will be 28 days. In other words, the censoring time will be the earliest of study day of last on-study contact, study day of death, and last dose day of randomized study regimen plus 28 days.

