8.1. Statistical Methods

8.1.1. Analyses of Time-to-Event Data

Comparisons of hazard functions in time-to-event analyses will be carried out via (linear) Cox proportional hazard models. Censoring conventions are given in [Section 7](#). A univariate analysis model containing only the single independent variable for treatment group will be calculated and reported.

In addition, the effects of adding other predictors to the Cox model, such as geographic region, age group, gender, and smoking status will be fully explored and reported.

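### SAP 8.2.1 attributes any difference between the two TNFi controls to geography, but in this two-stratum contrast region and TNFi agent are the same variable

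*SAP*

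**What the plan says.** The control arm pools two agents assigned by country. Protocol 1.2 says "Subjects randomized to receive TNFi in the United States (US), Puerto Rico and Canada will receive adalimumab", and Protocol 3 says "in all other countries, subjects randomized to TNFi will receive etanercept 50 mg once weekly by SC injection". SAP 2.1 repeats this.

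For the co-primary endpoints, SAP 8.2.1 adds an analysis by TNFi subset as a consistency check and defines the strata as "USA/Puerto Rico/Canada as one stratum, the rest as the other stratum". It then says "No additional analyses comparing adalimumab vs. etanercept will be conducted for the purpose of reporting the primary endpoints of the study". The same sentence ends with the rule at issue: when the primary endpoint analyses are reported, "any difference in hazard ratio between the two TNFi controls will be attributed to geographic difference".

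Protocol 9.2.1 plans the same stratum analysis, also as a consistency check, but gives no rule on what would cause a difference. The attribution appears only in the SAP, and neither document gives a reason for it.

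**The concern.** The rule assigns a cause before the data are seen. No country supplies both agents, and the strata are drawn along the same line as the agents. If the strata disagree, the trial has no internal information on whether the reason is where the patients were treated or which TNFi they received. Chance could also produce a difference, yet the rule covers any difference.

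The stratum analysis is the planned check that a mixed TNFi comparator gives consistent results for MACE and for malignancy. If the results diverged, a reader would want to know that they may depend on the TNFi used. Under the rule, the report would instead state geography as the explanation.

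**Working it through.** **Plan's own figures.** No figure is in dispute. The event targets in Protocol 9.1 reproduce from (z for two-sided 5% + z for power)² / [(2/3)(1/3)(ln 1.8)²]:

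- 90% power: (1.960 + 1.282)² / (0.2222 × 0.3455) = 136.9, so 137 (stated 138).
- 80% power: (1.960 + 0.842)² / (0.2222 × 0.3455) = 102.2, so 103 (stated 103).

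The stratum split does not enter the formula, so the targets do not depend on this point.

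**Inputs.** Agent by country (Protocol 1.2 and 3; SAP 2.1); the two strata and the attribution rule (SAP 8.2.1); the region covariate (SAP 6.4 and 8.1.1). Call the US/Puerto Rico/Canada stratum A and the rest B.

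**Reading 1: the tofacitinib-versus-TNFi hazard ratio differs between strata.** Let bA and bB be the baseline log hazards, t the tofacitinib effect, g the adalimumab-versus-etanercept effect, and i the regional modification of the treatment effect in A.

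| Cell | Log hazard |
|---|---|
| A, tofacitinib | bA + t + i |
| A, TNFi (adalimumab) | bA + g |
| B, tofacitinib | bB + t |
| B, TNFi (etanercept) | bB |

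There are five unknowns and four cells, and the design matrix has rank 4. Adding any constant to both g and i and subtracting it from bA leaves every cell unchanged.

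- Log hazard ratio in A: (bA + t + i) − (bA + g) = t + i − g.
- Log hazard ratio in B: t.
- Difference: **i − g**.

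Only the difference between regional modification and agent effect can be estimated. Keeping the two tofacitinib doses apart does not help: over the six cells, the agent column is identical to the stratum-by-TNFi column (rank 5 for 6 columns).

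Illustration with assumed stratum hazard ratios of 1.5 in A and 1.0 in B, so i − g = ln 1.5 = 0.405:

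- Regional modification 1.5, no agent difference: 0.405 − 0.
- No regional modification, agent hazard ratio 0.667: 0 − (−0.405).
- Both, 1.225 and 0.816: 0.203 − (−0.203), which is 0.405 up to rounding.

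The data would look the same in all three cases. On this reading baseline risk cancels: doubling the hazard in both arms of A adds ln 2 to each and leaves the stratum hazard ratio at t + i − g. A regional difference in background risk alone therefore largely fails to explain a difference.

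**Reading 2: the hazard of one control relative to the other.** The contrast is (bA + g) − bB = (bA − bB) + g. Baseline risk does not cancel here, so geography is a direct candidate, but it is still added to the agent effect. Within the TNFi arm, intercept, region and agent have rank 2 for 3 columns. The tofacitinib arms give (bA − bB) + i. Subtracting this leaves g − i, the same unresolved quantity with its sign reversed. Separating the parts requires assuming i = 0, and the SAP states no such assumption.

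**Does the region covariate help?** SAP 8.1.1 will explore "the effects of adding other predictors to the Cox model, such as geographic region", with four levels in SAP 6.4: USA/Canada, Europe, Latin America and rest of world. No interaction with treatment is named. Even if one were fitted, the last three levels lie mainly or wholly in etanercept countries (the level for Puerto Rico is not stated). The model could show regional variation where the agent is constant. It could not show why the adalimumab stratum differs from the etanercept stratum.

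**The case against.** The strongest reply is that the clause is a cautious convention. The two agents were not randomised against each other, and the SAP wants to prevent an informal comparison between them. That caution is sound, but the preceding clause, which bars agent comparisons, already secures it. The attribution goes further and asserts one cause, to the exclusion of the agent and of chance.

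A second reply is that regions do differ in background risk. This has no force on the first reading, where baseline risk largely cancels. It has force on the second, where geography is a plausible explanation but still cannot be told apart from the agent. The wording of the clause fits either reading, and the aliasing holds on both.

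A third reply is that region and agent are not confounded everywhere. This stands: regional variation can be studied within the etanercept countries. The point must therefore be confined to the two-stratum contrast. A reader might infer that the trial can say nothing about regional differences; the four-level covariate in SAP 6.4 shows otherwise.

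A fourth reply is that the practical effect is small. It is limited: the SAP openly labels the strata by the agent used, and the rule governs interpretation only. That affects how much weight the point carries, not whether the clause is right.

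**Conclusion.** The attribution clause is wrong as written. In the comparison of the adalimumab stratum with the etanercept stratum, region and agent are fully aliased at any event count, and no statement elsewhere in the documents supplies an assumption that would separate them. This conclusion needs only that the agent follows country and that the strata follow the same line, both of which the documents state. The hazard ratios of 1.5 and 1.0 are assumed for illustration.

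The scope is the interpretation of one consistency analysis for the two co-primary endpoints. Three stronger inferences are not supported:

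- That the primary result is compromised. The pooled hazard ratio compares tofacitinib with the TNFi supplied locally, and the rule in SAP 4.2 ("Non-inferiority of tofacitinib regimens to TNFi control regimen will be concluded if the upper confidence limits for both malignancy" and MACE are below 1.8) does not use the attribution.
- That a difference between strata should be read as an agent effect. The design cannot identify that cause either.
- That the stratum hazard ratios are free of other assumptions because treatment was randomised within strata. The Safety Analysis Set leaves out subjects who were randomised but never dosed (SAP 5.3 and 5.4), and both time definitions in SAP 7.1.1 involve censoring. The point here does not depend on that.

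**What to change.** In SAP 8.2.1, keep the bar on adalimumab-versus-etanercept analyses and the lead-in that limits the sentence to reporting of the primary endpoints. Replace the attribution with wording such as:

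> *a difference between the TNFi strata in hazard ratio may reflect region, the TNFi used, or chance; region and TNFi agent cannot be separated in this comparison.*

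The cost is one reworded SAP clause. It needs no new data, no additional analysis and no change to the primary analysis. Protocol 9.2.1 can stay as it is, since it states no cause.
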